6 STATISTICAL METHODOLOGY FOR EFFICACY

6.1 *Planned analyses and definitions*

6.1.1 *Primary endpoint analysis*

Objective response is defined as having partial remission (PR) or better as best overall response based on the the Lugano classification response criteria per independent review. The **objective response rate (ORR)** is calculated as the number of objective responders divided by the number of patients in the “Per Protocol Patients” analysis set.

6.1.2 *Secondary endpoints analyses*

The **overall response rate (ORR)** is calculated as the number of objective responders based on the the Lugano classification response criteria per independent review divided by the number of patients in the “All Evaluable Patients” and “All Treated Patients” analysis sets.

The **overall response rate (ORR)** is calculated as the number of objective responders based on the investigator criteria divided by the number of patients in the “Per Protocol Patients”, “All Evaluable Patients” and “All Treated Patients” analysis sets.

The **complete remission rate** is calculated as the number of patients with complete remission based on the the Lugano classification response criteria per independent review or per investigator assessment divided by the number of patients in the “Per Protocol Patients”, “All Evaluable Patients” and “All Treated Patients” analysis sets.

The **duration of response (DoR)** will be analyzed in the “All Responder Patient”. Duration of response will be calculated from the date of first documentation of response to the date of disease progression, recurrence or death with the same censoring rules as PFS. Response will be assessed according to the Lugano classification response criteria per independent central review and investigator assessment.

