Progression-free survival (PFS) is defined as the time from the date of first administration to the date of documented progressive disease (PD) or death (regardless of the cause of death). If the patient receives further antitumor therapy (including stem cell transplant) before, PFS will be censored on the date of the last disease assessment prior to the administration of this antitumor therapy. If the patient is lost to follow-up for the assessment of progression the PFS will be censored at the date of last valid tumor assessment. If the patient does not received any drug infusion, he/she will be censored at time zero. Both, independent central review and investigator assessments, will be used for the determination of PFS.

Progression-free survival at 6/12 months (PFS6/PFS12), defined as the Kaplan-Meier estimate of the percentage of patients who are progression-free at six/twelve months after first administration; both independent central review and investigator assessment will be used for the determination of PFS.

Within-patient PFS/TTP, defined as the ratio of the PFS achieved with the experimental treatment versus prior last TTP. Intra-patient PFS/TTP ratio will be categorized and analyzed as a dichotomous variable. Clinical benefit will be defined if a >33% longer PFS/TTP with the experimental treatment vs. the TTP with the immediate prior chemotherapy (ratio >1.33) is achieved.

Overall survival (OS), defined as the time from the date of first administration to the date of death (of any cause) or last patient contact.

Overall survival at 6/12 months (OS6/OS12), defined as the Kaplan-Meier estimate of the percentage of patients who are alive at six/twelve months after first administration.

Treatment safety [AEs, serious adverse events (SAEs) and laboratory abnormalities] graded according to the NCI-CTCAE, v. 4. Dose reductions, skipped doses or dose delays required due to treatment-related AEs, and reasons for treatment discontinuations will be analyzed.

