8.6 Imputation of incomplete dates

The dates of certain historical or current clinical activities are key component for statistical analysis. Incomplete date appears when day, month or year is/are missing, and it could be imputed so that variables like time to and duration of certain event can be calculated. If none of day, month and year is available, then the date is missing, no imputation will be done.

Before treatment start date

If day of a date is unknown then the imputed day will be 15, if the month is also unknown then the imputed date will be July 1st. This assumption will be valid if the imputed date is earlier than the treatment start date; otherwise the imputed date will be the first day of the treatment start month.

Between treatment start and end of treatment

All date variables during treatment where information is needed and is not fully available, for example adverse events or concomitant medications, will be subject of imputation by means of SAS programming. If the day of a date is unknown then the imputed day will be 1, if the month and/or year is also unknown then the imputed date will 1/January. This assumption will be valid if the imputed date is earlier than the treatment start date; otherwise, the imputed date will be the treatment start date.

After end of treatment

To ensure the most conservative approach for the main time-to-event variables (i.e. PFS and OS) that can be affected by missing values the following rules will be implemented by means of SAS programming: if the day of a date is unknown then the imputed day will be 1; if the month is also unknown, then the imputed date will be 1/July. This assumption will be valid if the imputed date occurs later than the last drug administration date; otherwise, the imputed date will be the last drug administration date plus 1 day.

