12.3.2 Deaths

Table 12.3.2.1 Cause of death

Reason*	N	%
Malignant disease	X	X.X
Treatment-related adverse event		
Other		
Total		

(*) Denominator=Number of patients who died

Listing 12.3.2.2 Deaths

Patient id.	Death date	Cause	Comments	Autopsy	Autopsy report available	Number of cycles administered	Last infusion date	Time on treatment*	Time from Last dose**

(*)Time on treatment: defined as last infusion date plus 30 days, or date of death or subsequent therapy (whichever comes first) minus first infusion date. (**)Time from last dose defined as death date minus last infusion date.

Listing 12.3.2.3 Deaths due to AEs

Patient id.	Cycle	Preferred term code	Adverse event reported (verbatim)	Grade	Relationship	Onset date	Resolved date	Action

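### SAP 8.6 checks imputed post-treatment dates only against the last dose, so a partial new-therapy date can precede a documented progression (PFS/DoR event becomes a censoring) and a partial death date can precede the last contact alive

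*SAP*

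**What the plan says.** The post-treatment part of SAP 8.6 opens with its aim: "To ensure the most conservative approach for the main time-to-event variables (i.e. PFS and OS"). A missing day becomes the 1st of the known month. For a missing month, "if the month is also unknown, then the imputed date will be 1/July". The only validity check is "This assumption will be valid if the imputed date occurs later than the last drug administration date", and the only fallback is "otherwise, the imputed date will be the last drug administration date plus 1 day". The rule is to be programmed in SAS.

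Three other places use such dates:

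- **SAP 6.1.2, PFS.** If further antitumor therapy comes before the event, "PFS will be censored on the date of the last disease assessment prior to the administration of this antitumor therapy".
- **SAP 6.1.2, DoR.** Analysed "with the same censoring rules as PFS".
- **SAP 12.3.2, Listing 12.3.2.2.** "Time from last dose defined as death date minus last infusion date".

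OS runs from first administration to death or last contact. No rule covers an imputed death that precedes a recorded contact. The SAP's one cross-check against another form, the footnote to Table 11.1.3.2, concerns the pre-study progression date.

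**The concern.** The last dose is a weak lower limit for events that may come weeks or months later. Two errors follow from applying the text literally.

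1. **Therapy before progression.** A patient progresses, then starts new therapy in the same month, and the day of that start is missing. The therapy is moved to the 1st, ahead of the scan that showed progression. PFS is then censored at the previous scan. Losing a progression raises PFS, PFS6/12 and DoR, which is the opposite of a conservative rule.
2. **Death before last contact.** A patient seen alive later in the month, or later in the year if the month is missing, can be given an earlier death date. The order of dates is impossible.

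A SAS program that follows the text would produce both without raising a query.

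**Working it through.** The documents give no figure for this rule, so there is none to reproduce. The lags, contact intervals and shares of partial dates below are assumptions. Every calendar day is taken as equally likely.

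**Worked cases (assumed dates)**

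| Last dose | Known fact | Partial date | Imputed | Result |
|---|---|---|---|---|
| 15 Mar 2017 | PD 10 May 2017 | therapy, May 2017 (true 22 May) | 1 May | passes the check; 9 days before PD |
| 3 May 2017 | PD 10 May 2017 | same | 4 May (fallback) | still 6 days before PD |
| 15 Mar 2017 | alive 20 Sep 2017 | death, Sep 2017 | 1 Sep | 19 days before last known alive |
| 15 Mar 2017 | alive in Oct 2017 | death, 2017 | 1 Jul | months before last known alive |

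The fallback does not help. Last dose plus 1 day precedes PD whenever the last dose was at least 2 days before PD.

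**Therapy date, day missing.** SAP 6.1.2 censors only if therapy comes *before* the event, so same-day ties are not counted. For a lag of L days in a month of m days, the imputed date is strictly before PD when PD falls on day 2 to m − L. That is max(0, m − L − 1) days. Summed over seven 31-day months, four 30-day months and February (28 days):

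- L = 7: (7×23 + 4×22 + 20)/365 = 269/365 = 74%
- L = 14: (7×16 + 4×15 + 13)/365 = 185/365 = 51%
- L = 21: (7×9 + 4×8 + 6)/365 = 101/365 = 28%
- L = 28: (7×2 + 4×1 + 0)/365 = 18/365 = 5%
- L = 45 or more: 0%

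Enumerating 1,460 consecutive PD dates gives the same percentages, with the last dose either 14 or 60 days before PD. Counting ties would give 77/54/31/8%, but the censoring rule does not support that count.

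**Therapy date, month also missing.** The date 1 July precedes PD when PD falls after 1 July and therapy starts in the same year: (183 − L)/365. This is 48% at 7 days, 46% at 14 and 42% at 28.

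**Death date, last contact 1 to 122 days earlier (about four months).** There are 365 × 122 = 44,530 combinations.

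- Day missing: each month contributes (m − 1)(m − 2)/2. The total is 7×435 + 4×406 + 351 = 5,020, and 5,020/44,530 = 11%.
- Month missing: a death k days after 1 July contributes min(122, k − 1), for k = 1 to 183. The total is 7,503 + 60×122 = 14,823, and 14,823/44,530 = 33%.
- 1 July falls later than the true death date for 181/365 = 50% of month-missing deaths.

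**Events at risk.** With 50 progressors, a 14-day lag and the day missing for 5% or 10% of therapy dates: 50 × 0.05 × 0.51 = 1.3 and 50 × 0.10 × 0.51 = 2.6, so about 1 to 3.

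**Effect on PFS6 (illustrative simulation).** Inputs: 60 patients, all progressing and all switching 14 days later, and 400 trials per setting. With 10% of therapy days missing, about 3 events are lost. Mean PFS6 goes from 7.4% to 7.6% at a median of 1.6 months (the earlier PTCL cohort, protocol Table 1), and from 30.9% to 33.1% at an assumed median of 3.6 months. With 30% missing, about 9 events are lost and PFS6 becomes 9.2% and 35.2%.

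**After the fix.** Flooring the therapy date at documented PD brings the share before PD to 0% at the three lags tested (7, 14 and 28 days).

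**The case against.** - **IRC dates.** Protocol 3.1 has the IRC assign progression and censoring dates by an algorithm in a separate charter. A reader might infer that documented progressions are lost from all PFS analyses. The documents do not show this: whether an imputed therapy date can override an IRC date cannot be read from them. This limit stands.
- **Frequency.** Protocol 5.10 places the EOT visit just before new therapy when therapy starts, which should often yield a full date. The telephone provision in protocol 5.2 covers survival only. Nothing documents how often dates are partial, so an upward bias in PFS of a given size is not established.
- **Which branch applies.** Under protocol 5.2, therapy or death within 30 days of the last dose itself defines EOT, so the post-treatment rule may not govern short lags. This is fair, but the on-treatment rule in SAP 8.6 has no progression or last-alive check either.
- **Direction.** Day 1 shortens OS for a day-missing death and PFS for a day-missing progression, so the conservative label fits those cases. It does not fit therapy dates or the 1 July rule.
- **Early deaths.** A day-missing death 31–60 days after last dose is placed within 30 days in about 49% of cases by enumeration. A reader might infer a distorted early-death rate. The SAP plans no such table; the effect is on a column of Listing 12.3.2.2.
- **Importance.** The time-to-event endpoints are exploratory in protocol 9.2.1 and SAP 6.2.2. Neither the 19/60 rule nor the futility rules use these dates.

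**Conclusion.** The gap is real and follows from the text. The last-dose check permits a day-missing therapy date before a documented progression in the same month, and SAP 6.1.2 then turns that event into a censoring. This is demonstrated for investigator-assessed PFS and DoR, and is conditional on the charter for the IRC versions. It contradicts the stated conservative aim for those dates. The death error gives an impossible order; with the day missing it shortens OS, while with the month missing it can go either way.

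The per-date percentages depend only on the calendar and the assumed lag or contact interval. The number of affected patients depends on the share of partial dates, which the documents do not give; 1 to 3 lost events is a scenario, not an estimate. The consequences are confined to secondary or exploratory endpoints and the death listing. The correction is worth making because it is cheap and the rule will be run by program.

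**What to change.** Keep the day-1 and 1-July defaults and add chronological limits to SAP 8.6:

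- **(a) Death:** the later of the imputed date and the day after last known alive.
- **(b) Progression:** the later of the imputed date and the day after the last assessment without progression.
- **(c) Subsequent therapy:** not before the day after last dose. Also not before a documented progression, whenever the known part of the therapy date is compatible with a start on or after that progression and the records do not show that therapy came first. This applies whatever the reason treatment stopped, so that patients who progress in follow-up and then switch are covered.
- **(d) All imputed dates:** stay within the known month and year, and do not exceed the data cutoff or any later known date that bounds the event. Where (a) or (b) would leave the known month, use the bounding day itself.
- **(e) EOT:** apply an EOT floor only where EOT is not itself defined by the imputed therapy or death date. Use the same limits under whichever 8.6 branch is applied to events within 30 days of the last dose.

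Limit the claim of conservatism so that it does not cover therapy dates or the 1 July rule. State whether imputed therapy dates enter the IRC algorithm, and report how many dates were imputed.

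The cost is SAP wording and a few lines of SAS, with no new data.

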8.7 Subgroup analyses

No specific subgroup analysis is planned for efficacy. However, the influence of prognostic factors on the efficacy endpoints will be studied in the multivariate analysis.

No formal statistical allowance will be made for multiple subgroup investigations, but any apparent subgroup interactions will be interpreted appropriately in a cautious way.

Analysis of safety profile by age, gender, race and body mass index (BMI) will be provided as specified in section 12.7.

Handling of multicenter data

Not applicable.

Handling of multiple comparisons

No formal statistical allowance will be made for multiple comparisons, therefore any apparent subgroup analysis will be interpreted appropriately in a cautious way.

8.8 Decimal places and methods for handling missing data

By default, all results will be rounded to one decimal, except in the case where variables are integer; in that case, they will be reported without decimals, for example, age in years, number of sites. For representing p-values four decimals will be selected as default but they could be rounded to fewer decimals if necessary. Missing values will not be included in the calculation of outputs.

8.9 Interim and group sequential analyses

Two futility analyses of the primary endpoint (ORR according to the Lugano classification response criteria per independent review) are planned to reject the alternative hypothesis when ~25% and ~50% of the patients have been recruited (first 15 and 30 patients, respectively). Pocock boundary and the actual number of patients confirmed by central pathological review will be used to control type II error for both analyses. For example, if there are two or less responders out of 15 patients or seven or less responders out of 30 patients, according to boundaries and sample size assumptions, the alternative hypothesis could be rejected, and thus recruitment might be stopped at the time of the first or second futility analysis, respectively.

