Two futility analyses of the primary endpoint (ORR according to Lugano classification response criteria and per IRC) are planned around six months after approximately 25% and 50% of eligible patients (i.e., 15 and 30 patients respectively with AITL confirmed by central pathological review) have been treated. Two or less responders out of 15 patients or seven or less responders out of 30 patients, according to boundaries and sample size assumptions, will mean that the alternative hypothesis could be rejected, and thus recruitment might be stopped at the time of the first or second futility analysis, respectively. Otherwise, accrual will continue to a total of 60 patients with AITL confirmed by central pathological review. This decision will be taken at the time by an Independent Data Monitoring Committee (IDMC). The IDMC, which will include specialists in PTCL supported by a medical statistician, will review data provided by the Investigators, the IRC efficacy assessments and safety information and will advise whether the study should continue. Recruitment can continue during the review period.

If there are 19 or more responders over the total of 60 patients, the efficacy of plitidepsin will be considered as clinically relevant in AITL patients.

Operational details for the IRC and IDMC will be detailed in the corresponding charters.

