## 5.6 CENTRAL PATHOLOGICAL REVIEW

Central pathological review will be conducted by experienced pathologists appointed by the Sponsor and available to the investigative sites for consultation about AITL diagnosis confirmation. Central pathological review is required for (a) local histopathology reports prior to patient treatment, and (b) tumor samples before each futility analysis and at the end of the study: see also [Figure 3. Study design](#).

The central laboratory pathologists will be responsible for (a) approving patient inclusion on the basis of investigative site pathology reports provided during screening, (b) analyzing tumor biopsies (initial diagnosis and/or relapses) to confirm the AITL diagnosis, and (c) analyzing blood samples to identify plasma biomarkers and extract DNA.

Tumor samples (initial diagnosis and relapses) are required for central review to confirm AITL diagnosis but not to approve inclusion. Archived tissue samples of representative tumors must be sent for central review and biomarker analysis. If the diagnosis biopsy is not available (because the patient was diagnosed at another site, for example), the most recent representative biopsy (relapse and/or progression) will be used. Submitting both, however, is strongly recommended. Tumor blocks will be returned to the centers.

Samples requirements are as follows:

- Archived tissue samples of representative tumors:
  - A formalin-fixed paraffin-embedded (FFPE) tissue block (preferred), usually from lymph node excisional biopsy.

or

- Freshly-cut unstained tumor slides.
- One whole blood sample for germline DNA extraction (6 mL) and another blood sample (4 mL) to obtain plasma are required for biomarker analyses: 10 mL will be collected in EDTA tubes will be collected at the same time as the first PK sample (prior to infusion) on Day 1 of Cycle 1.

Central pathological confirmation of AITL diagnosis for the 15 and 30 patients in the futility analyses is mandatory and for all patients at the end of the study; the central review pathologists will also be available when required for consultation in controversial cases and at the investigators' discretion.

Tissue sample specifications (number and thickness) must be confirmed in advance with the central laboratory. Procedures for collection, handling, and shipping of the samples will be provided in a separate instruction manual for sites.

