## **5.13 INDEPENDENT DATA MONITORING COMMITTEE**

An independent expert advisory group commissioned by the Sponsor will evaluate efficacy and safety data in enrolled patients. The primary objectives of this Independent Data Monitoring Committee (IDMC) are as follows:

- To maintain the integrity of the trial conduct, to evaluate risk/benefit where possible of the APL-B-021-13 patients by monitoring the efficacy and safety data and making recommendations regarding treatment continuation and options for those on active treatment.
- To inform the Sponsor's Executive Committee regarding the outcome of the planned futility analyses as specified in the trial's Statistical Analysis Plan (SAP) and to make recommendations.

The IDMC's procedures will be detailed in a separate charter: investigators may be expected to provide complete and timely patient data for committee meetings in addition to normal CRF data entry.

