Radiological tumor assessment will be performed by PET-CT in combination with diagnostic quality CT one to two weeks after last dose of Cycle 3 and at least four weeks after last dose of Cycle 6 (but no more than eight weeks), and by CT-scan every four months (+ two weeks) for the first two years, and every six months (+ two weeks) thereafter or at suspected clinical progression, unless otherwise clinically indicated. An IRC consisting of medical specialists (radiologists and hematologists) who are directly involved in the care of patients with AITL—but not investigators in this trial—will review all efficacy data (including radiological assessments, bone marrow biopsies) and will assign the best response and the date of objective response or progression/censoring according to their independent evaluation.

Two futility analyses of the primary endpoint (ORR according to the Lugano classification criteria and per IRC) are planned for the time six months after ~25% and ~50% of eligible patients have been treated (i.e., 15 and 30 patients, respectively). For example, if there are two or less responders out of 15 patients or seven or less responders out of 30 patients, according to boundaries and sample size assumptions, the alternative hypothesis could be rejected, and thus recruitment might be stopped at the time of the first or second futility analysis, respectively. Otherwise, accrual will continue to a total of 60 patients with AITL confirmed by central pathological review. This decision will be taken at the time by an IDMC. The IDMC, which will include specialists in PTCL supported by a medical statistician, will review data provided by the

---

 When PET-CT is performed it must be in combination with diagnostic quality CT with intravenous contrast (except medically contraindicated). Two alternatives are allowed: Hybrid PET CT scanners may be used to acquire diagnostic quality CT which includes intravenous contrast OR PET CT without intravenous contrast and diagnostic quality CT images with intravenous contrast using a standalone CT scanner must be performed.

Investigators, the IRC efficacy assessments and safety information and will provide advice on whether the study should continue.

Operational details (including procedures for review data submission) for the IRC and IDMC will be detailed in the corresponding charters.

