## **9.3 INTERIM ANALYSIS**

Two futility analyses of the primary endpoint (ORR according to the Lugano classification criteria and per IRC) are planned to reject the alternative hypothesis six months after approximately 25% and 50% of eligible patients have been treated (15 and

30 patients, respectively). Pocock boundary and the actual number of patients confirmed by central pathological review will be used to control type II error for both analyses. An IDMC, which will include specialists in PTCL supported by a medical statistician, will review data provided by the Investigators, the IRC efficacy assessments and safety information and will provide advice on whether the study should continue. For example, if there are two or less responders out of 15 patients or seven or less responders out of 30 patients, according to boundaries and sample size assumptions, the alternative hypothesis could be rejected, and thus recruitment might be stopped at the time of the first or second futility analysis, respectively. Otherwise, accrual will continue to a total of 60 patients with AITL confirmed by central pathological review. Active recruitment will not be halted while the analysis is being carried out.

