2 STUDY DESIGN

Prospective, multicenter, phase II clinical trial.

The aim of this clinical trial is to determine the efficacy of plitidepsin in patients with relapsed/refractory AITL. A total of 60 patients will receive plitidepsin. The primary endpoint will be the ORR according to the Lugano classification response criteria per independent central review.

An Independent Review Committee (IRC) consisting of medical specialists (radiologists and hematologists) who are directly involved in the care of patients with AITL but do not take part in this trial as investigators or sub-investigators, will review all efficacy data and will assign the date of objective response or progression/censoring according to their independent evaluation.

Two futility analyses of the primary endpoint (ORR according to Lugano classification response criteria and per IRC) are planned around six months after approximately 25% and 50% of eligible patients (i.e., 15 and 30 patients respectively with AITL confirmed by central pathological review) have been treated. Two or less responders out of 15 patients or seven or less responders out of 30 patients, according to boundaries and sample size assumptions, will mean that the alternative hypothesis could be rejected, and thus recruitment might be stopped at the time of the first or second futility analysis, respectively. Otherwise, accrual will continue to a total of 60 patients with AITL confirmed by central pathological review. This decision will be taken at the time by an Independent Data Monitoring Committee (IDMC). The IDMC, which will include specialists in PTCL supported by a medical statistician, will review data provided by the Investigators, the IRC efficacy assessments and safety information and will advise whether the study should continue. Recruitment can continue during the review period.

If there are 19 or more responders over the total of 60 patients, the efficacy of plitidepsin will be considered as clinically relevant in AITL patients.

Operational details for the IRC and IDMC will be detailed in the corresponding charters.

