5 SAMPLE CONSIDERATIONS

The primary endpoint for this study is ORR according to the Lugano classification response criteria per independent review in “Per Protocol Patients” population.

A total of 60 patients with AITL confirmed by central pathological review will be treated, 19 or more responders will be needed to get an overall estimate for response rate higher than 30% and its lower limit for the 95% confidence interval greater than 20% (31.7% CI95% 20.3%–45.0% following the binomial distribution).

The type I error (alpha) associated with this one-sided test is 0.025 and the type II error (beta) is 0.1; hence, statistical power is 90%. The null hypothesis (H0) is set at $ORR \leq 20\%$ ($P_0=0.208$) versus the alternative hypothesis (H1) at $\geq 40\%$ patients ($P_a=0.41$) having an objective response, the variance of the standardized test is under the null hypothesis.

Two futility analyses of the primary endpoint (ORR according to Lugano classification and per IRC) are planned to reject the alternative hypothesis six months after 25% and 50% of eligible patients have been treated (15 and 30 patients, respectively). Pocock boundary and the actual number of patients confirmed by central pathological review will be used to control type II error for both analyses. For example, if there are two or less responders out of 15 patients or seven or less responders out of 30 patients, according to boundaries and sample size assumptions, the alternative hypothesis could be rejected, and thus recruitment might be stopped at the time of the first or second futility analysis, respectively. Otherwise,

accrual will continue to a total of 60 patients AITL confirmed by central pathological review. Active recruitment will not be halted while the analysis is being carried out.

Therefore, if there are 19 or more responders of 60 patients, the null hypothesis can be rejected, allowing consideration of the observed activity plitidepsin as clinically relevant in the setting of patients with AITL.

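### SAP 8.9 triggers the two futility looks at recruitment of the first 15 and 30 patients, whereas SAP 2, SAP 5 and the protocol wait about six months after 15 and 30 eligible patients have been treated

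*SAP*

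**What the plan says.** SAP 8.9 says the looks are "planned to reject the alternative hypothesis when ~25% and ~50% of the patients have been recruited (first 15 and 30 patients, respectively"). It gives no follow-up interval and does not require that the patients be treated.

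SAP 5 uses almost the same sentence with a different trigger: "planned to reject the alternative hypothesis six months after 25% and 50% of eligible patients have been treated (15 and 30 patients, respectively"). SAP 2 has the looks "planned around six months after approximately 25% and 50% of eligible patients" with centrally confirmed AITL have been treated. Protocol 9.3 has "six months after approximately 25% and 50% of eligible patients have been treated". The synopsis and Protocol 3, 8.1 and 9.1 agree, and Protocol 3 identifies the patients as "eligible patients (i.e., 15 and 30 patients respectively with AITL confirmed by central pathological review) have been treated".

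Protocol 5.13 has the IDMC inform the sponsor "regarding the outcome of the planned futility analyses as specified in the" SAP, so the document it points to holds both timings.

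Four other provisions bear on the point:

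- Protocol 8.1 schedules the first response scan "one to two weeks after last dose of Cycle 3".
- Protocol 5.6 states: "Central pathological confirmation of AITL diagnosis for the 15 and 30 patients in the futility analyses is mandatory".
- SAP 6.1.1 divides responders by all Per Protocol patients, and the interim tables in SAP 11.3.1 have a row for NE.
- SAP 5 and SAP 8.9 base the Pocock boundary on the number of centrally confirmed patients and give 2/15 and 7/30 as example cut-offs.

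**The concern.** A look triggered by recruitment of patient 15 or 30 includes patients who have not reached their first scan. They cannot be responders yet, but under SAP 6.1.1 they stay in the denominator. The boundary adjusts for how many patients are confirmed, not for how many have been assessed. Each such patient can only lower the responder count, so an active drug crosses the futility cut-off more often than the design allows. These looks inform the IDMC's advice on stopping recruitment, and the stated 90% power depends on them.

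**Working it through.** **Inputs.** From SAP 5: one-sided alpha 0.025, power 90%, H1 at 40% (Pa = 0.41), success at 19 or more of 60. From SAP 5 and 8.9: example cut-offs of 2 or fewer of 15 and 7 or fewer of 30. From Protocol 5.1: 36 months of enrollment. Even accrual is an assumption.

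**1. The plan's own figures.** The exact 95% interval for 19/60 (31.7%) is 20.3% to 45.0%, as stated. With all responses known, let X1 ~ Bin(15, p), X2 = X1 + Bin(15, p) and X = X2 + Bin(30, p).

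- Crossing = P(X1 ≤ 2) + P(X1 ≥ 3 and X2 ≤ 7).
- Power = P(X1 ≥ 3, X2 ≥ 8 and X ≥ 19).

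At p = 0.40, crossing is 2.7% at the first look plus 3.1% at the second, 5.9% before rounding, and power is 89.5%. At p = 0.41 they are 4.8% and 91.7%. The stated 90% is therefore reproduced when all 15 and 30 responses are known.

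**2. When the first response can be seen.** Cycle 3 Day 15 is 28 + 28 + 14 = 70 days after first dose. The scan follows 7 to 14 days later, on days 77 to 84.

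**3. How many patients are unscanned.** Sixty patients in 36 months is one per 36 × 30.44 / 60 = 18.3 days. If first dose is on the day of recruitment, then at a same-day cut the latest patients are at days 0, 18, 37, 55, 73 and 91, so 5 are unscanned. A later cut shifts these days by the lag: 14 days leaves 4, 30 days leaves 3, and 60 days leaves 1 (scan at day 77) or 2 (scan at day 84). At 84 days none is left.

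**4. Effect on the looks.** With k unscanned patients counted as non-responders at each look, X1 ~ Bin(15 − k, p), X2 = X1 + Bin(15, p) and X = X2 + Bin(30 + k, p), with cut-offs 2, 7 and 19 unchanged. Every response is assumed visible at the Cycle 3 scan.

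| k | Lag to data cut | Crossing, p = 0.40 | Power, p = 0.40 | Crossing, p = 0.41 | Power, p = 0.41 |
|---|---|---|---|---|---|
| 0 | 84 days | 5.9% | 89.5% | 4.8% | 91.7% |
| 1 | 60 days (scan day 77) | 7.9% | 87.9% | 6.5% | 90.3% |
| 2 | 60 days (scan day 84) | 10.6% | 85.7% | 8.9% | 88.3% |
| 3 | 30 days | 14.1% | 82.7% | 12.1% | 85.5% |
| 4 | 14 days | 18.6% | 78.7% | 16.3% | 81.7% |
| 5 | same day | 24.3% | 73.5% | 21.7% | 76.6% |

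**5. Type I error.** At p = 0.20 the chance of success is 2.2% without looks, 1.9% with complete data at the looks and 1.2% with k = 5. It is not inflated.

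**6. The six-month timing.** Six months is about 183 days. The Cycle 3 scan is then past due even with two two-week cycle delays (84 + 28 = day 112); Protocol 7.4 allows longer delays only with sponsor approval. Cycle 6 Day 15 is 5 × 28 + 14 = day 154, and its scan falls 28 to 56 days later, on days 182 to 210. On even accrual the latest patients are at days 183, 201 and 219, so 2 may still await that scan if cycles are not delayed.

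**The case against.** The best counter-reading is that 8.9 only names the cohort and leaves the timing to SAP 5. It also asks for independent review and centrally confirmed patients, which takes time, so a same-day cut is hardly achievable. That stands as a limit on the size, and a 60-day lag costs only about 2 to 4 points of power at 40%. It does not remove the conflict, because the words in 8.9 set a time and that time differs from SAP 5.

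A second objection is that SAP 8.8 leaves missing values out of calculations, so unscanned patients might be dropped rather than counted as NE. With the cut-offs kept at 2 and 7 this changes nothing, because crossing depends only on the responder count. The loss shrinks if the cut-offs are also rescaled to the number assessed. For 10 and 25 assessed patients, cut-offs of 1 and 5 give 6.5% crossing and 88.4% power at 40%; cut-offs of 1 and 6 give 10.0% and 85.9%. But SAP 5 and 8.9 tie the boundary to the number centrally confirmed, so this rescaling is not in the plan.

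It is also true that the stop is advisory. The power figures hold only if the advice is followed. The IDMC and IRC charters, which were not available for this review, may add operational detail, but they cannot make two SAP sections agree.

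**Conclusion.** The concern holds. The SAP contains two triggers for the same looks, and 8.9 is the only place that differs from the protocol. The mismatch is certain from the text alone. The power loss is an illustration that rests on even accrual, first dose at recruitment, unscanned patients counted as non-responders, fixed cut-offs and the IDMC's advice being followed. On those terms, power at an ORR of 40% falls from 89.5% to between 73% (same-day cut) and 88% (60-day lag), with no loss from 84 days on. The same-day figure is the upper end, not the expected effect. Type I error and the 19/60 success rule are not harmed. This should be corrected before the looks are run.

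**What to change.** Reword the trigger in SAP 8.9 to match SAP 5 and Protocol 9.3: six months after the 15th and 30th eligible, centrally confirmed patients have been treated, with all of those 15 or 30 in the denominator. State there that each look uses best response to date, in line with SAP 6.1.1. Improvements first seen at a pending Cycle 6 scan, about the last 2 patients on even accrual, would then not count at that look.

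The cost is one sentence in SAP 8.9. The looks stay where SAP 2, SAP 5 and the protocol already place them, and the sample size and cut-offs are unchanged.
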